6.7 Inclusion/Exclusion Criteria

Inclusion criteria:

1. All ages and both genders
2. Wounds of a similar type, size, location and bleeding tendency listed in Table 1.
3. Currently on anticoagulation therapy with no dosage limitations.
4. Diagnosed with a coagulation disorder.
5. Participants must be able to participate for the 30 day duration of the study.

Exclusion criteria:

1. Any clinically infected wound, draining pus, surrounding erythema or edema, or patients with systemic signs of infections.
2. Subjects on antibiotic therapy prior to enrollment.
3. Subjects with known allergy to bovine proteins, atopic reactions, history of anaphylaxis.
4. HIV virus infection
5. Sensitivity to iodine
6. Inability to give informed consent.
7. Inability to return for a 30 day follow-up visit.

6.8 Source of Research Material

6.9 Number of Subjects: A total of 200 subjects, are to participate in this study.

7.0 Recruitment: Subjects will be randomly selected from within each participating surgical department at Edgardo Rebagliati Martins National Hospital, Guillermo Almenara I. EsSalud National Hospital, Peruvian Air Force Hospital, and the Military Hospital of Peru. The faculty from all of the hospitals will obtain an informed consent, prior to their participation in the study. No promotional fliers are planned. The consent form will be provided by the hospitals in Spanish. Subjects will not be paid for participation in this study.

7.1 Benefits: The possible benefit of the patient's participation in this study is a faster time to clotting, less blood loss, faster wound healing, and less loss of tissue. However, the participant should understand there is no guarantee or promise that they will receive any benefit from this study, other than knowing that the information may help future patients.

7.2 Risks: The risks of application of SeraSeal are theoretical. These risks may be bleeding, infection, and allergic reaction¹⁴. Anaphylaxis is a possible risk, but the incidence is not clearly known. In clinical case studies, SeraSeal was used in Greece on 39 dialysis patients¹⁵. These patients received SeraSeal 3-4 times each over a period of two weeks, and no reactions or adverse sequel were noted¹⁶. Aprotinin, a bovine protein derived from the bovine lung, is used in cardiac surgery and is the component of some fibrin sealants. It has an anaphylaxis rate of 2.5% on second exposure, with a mean interval of 1,654 days (range, 16-7,136 days)^{16,17}. SeraSeal contains no aprotinin. Bovine gelatin is a component of some vaccines and anaphylaxis has been reported with this protein¹⁸. Other bovine proteins for which anaphylaxis and hypersensitivity reactions have been reported, are bovine serum albumin¹⁹, thrombin^{20,21}, recombinant Factor VIII²², insulin²³, and tissue sealants²⁴. The risk of anaphylaxis appears to be lower for topical devices than injected ones, and repeated administration with a break, as proposed in this study, also appears to have a lower incidence of anaphylaxis²⁵. We surmise that anaphylaxis may be a risk of application of SeraSeal. Measures to reduce and treat anaphylaxis are to exclude those patients who are sensitive to bovine proteins from the study, and to provide a crash cart, and/or any additional standard and customary treatment(s). One of the purposes of this study is to determine that risk. Reports of an autoimmune reaction to fibrin sealants containing bovine Factor V mimicking hemophilia have been reported. SeraSeal does not contain Factor V.

7.3 Safeguards for Protecting Subjects: The risks of SeraSeal treatment are minimized by the patient selection

process. Should an allergic reaction occur, the participant will be withdrawn from the study and standard of care will be administered. Physicians, nurses, and technicians, will be on hand for all procedures. Patients will be monitored through routine post-operative care. Should any adverse event occur during treatment, immediate intervention will be taken. A crash cart is kept in the treatment room and on the hospital floor. Patient records will be kept confidential.

7.4 Alternatives: Alternatives to SeraSeal are the application of no hemostatic agents, electric cauterization, ligature, pressure dressings, collagen dressings, and the use of fibrin sealants.

8.0 Data Analysis:

8.1 Data Collection: There will be one study form for each patient. The surgery form will have all of the outcome data, including blood loss and complications. Once a patient is placed on the surgery schedule, the patient will be asked to participate in the clinical trial by the participating investigator surgeon. The only patients that will require special action are the SeraSeal patients. For those patients the need for SeraSeal will be made known only to the attending surgeon and/or fellows, and made available to the OR room. At the time of the pre-op exam, the inclusion/exclusion of participation in the study will be filled out. The research nurse will collect all data forms and will be responsible for evaluating them for completeness and accuracy, except for time to hemostasis supplied by the surgeon.

8.2 Statistical Analysis: We will compare continuous outcomes such as time to hemostasis (primary outcome), pre and post operative blood loss, surgery duration, (log) bacterial titer, and length of hospital stay in SeraSeal versus conventional treatment, using factorial analysis of variance (ANOVA) methods.

For continuous lab outcomes measured on four occasions (base, 24 hours, 48 hours, 30 days), we will use repeated measure analysis of variance methods to compare mean lab values for conventional versus SeraSeal overall.

For binary outcomes, (including adverse event outcomes) that are not quantified or that may be dichotomized for clinical convenience and interpretability such as fever (yes or no) or pruritus (yes or no) we will use chi-square methods to compare conventional versus SeraSeal treatment proportions overall. Since the total follow up times may differ between groups, we will also compare rates per person-time of binary outcomes under conventional versus SeraSeal treatment overall.

Sample size: The sample size is based on the primary outcome, time to hemostasis. We consider at least a 25% mean reduction in time to hemostasis to be the smallest clinically important average improvement. Historically, the mean time to hemostasis for liver surgery is 30 minutes. A 25% reduction from 30 minutes corresponds to a mean time to hemostasis of $30 \times 0.75 = 22.5$ minutes under SeraSeal. Based on this calculation, a sample size of 20 persons per group provides 80% power for confirming this mean difference using the $p < 0.05$ two sided significance criterion ($\alpha = 0.05$). Assuming that all of the surgical procedures can be collapsed within their respective departments, and assuming that the 25% mean difference or greater difference occurs in all 5 departments, the required total sample size is $20 \times 2 \times 5 = 200$.

9. Duration of Study: Subject participation is 30 days post study procedure. Expected enrollment time is 12 months.

10. Bibliography:

1. Cantril SV, Facial Trauma. In Rosen (ed): Emergency Medicine: Concepts and Clinical Practice, 4th ed., copyright 1998 Mosby-Year Book, Inc.
3. Dietrich W, Spath P, Zuhlsdorf M, Dalichau H, Ickirchhoff PG, Kuppe H, Preiss DU, Mayer G. Anaphylactic reactions to aprotinin re-exposure in cardiac surgery; relation to antiaprotinin

- immunoglobulin G and E antibodies. *Anesthesiology* 2000 Jul; 95 (1): 64-71; discussion 5A-6A.
 6. FDA: Transcript of Safety and Efficacy of Methods for Reducing Pathogens in Cellular Blood Products Used in Transfusion Workshop, 8-7-02.

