12.1 STUDY INFORMATION

12.1.1 Protocol

Study No.: WLI-1196-PER

Clinical Investigation - Lima Peru

1. **Title:** Efficacy and Safety Investigation of SeraSeal
2. **Principal Investigator: Thoracic & Cardiovascular:** [name]
[name]
[name] [name]
[name]
[name]
General Surgery: [name]
[name]
[name]
[name]
[name]
[name]
[name]
[name]
[name]
Head & Neck: [name]
[name]
Orthopedics: [name]
Neurosurgery: [name]
3. **Monitors:** [name]
Edgardo Rebagliati Martins National Hospital

[name] [name]
Edgardo Rebagliati Martins National Hospital
4. **This protocol focuses on treatment**
5. **Location:** Edgardo Rebagliati Martins National Hospital, Lima, Peru
Guillermo Almenara I. EsSalud National Hospital, Lima, Peru
[name] Casimiro Ulloa Emergency Hospital
FAP- Peruvian Air Force Hospital, Lima, Peru
Military Hospital of Peru, Lima
6. **Research Plan:**

6.1 Purpose: The purpose of this study is to investigate the safety and effectiveness of SeraSeal on clotting time in surgical or trauma wounds. This study is designed to determine whether it is safe and effective in achieving hemostasis in different types of wounds.

6.2 Hypothesis or Research Questions or Objectives: The null hypothesis is that cauterization is more effective than SeraSeal in achieving hemostasis. The alternative hypothesis is SeraSeal will achieve hemostasis sooner than cauterization. A secondary endpoint is the measurement of blood loss.

6.3 Significance: SeraSeal shows promise of being an effective hemostatic agent applicable to wounds, surgical operations in which hemostasis is difficult (hepatic, renal and splenic trauma, debridement, burns, skin grafting, endoscopic procedures), control of epistaxis, esophageal variceal bleeding, bleeding peptic ulcers, and bleeding associated with proctitis and cystitis. For some of these conditions, there is no entirely satisfactory treatment.

6.4 Relevance: The availability of an easy to use, stable, safe, effective hemostatic agent, would be a tremendous advantage to the trauma patient (surgical or accidental), possibly reducing morbidity and mortality significantly, and conserving surgical and blood resources.

6.5 Background and Review of Literature:

Problem with Bleeding Wounds

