This study is designed to determine whether SeraSeal is safe, effective, and will improve the quality of care, in achieving hemostasis in surgical wounds or other emergent hemorrhagic episodes. The effectiveness will be determined by achieving hemostasis after application of the product. The safety will be determined by monitoring outcomes from application: recurrence of bleeding, infection, lack of healing, and presence of hypersensitivity reactions, e.g. pruritus, fever, rash, anaphylaxis. An improved quality of care will be achieved by reducing or eliminating the hospital length of stay.

Characteristics of SeraSeal

SeraSeal is a bovine protein-derived accelerator of hemostasis interacting with the intrinsic and extrinsic pathways. It is obtained from pathogen and prion free cows. SeraSeal can be provided as a solution, spray, foam, incorporated into an absorbable dressing or a non-absorbable removable dressing. Its active ingredients are the bovine proteins Factors II, VII, IX, and X.

Toxicity of SeraSeal

A total dosage level of SeraSeal over 13,000 IU/Kg (2.4 mg protein) in leporids and canines had no adverse effects¹⁴. The total expected treatment levels to be used in this study is less than 1,000 IU/Kg, a 130 fold lower level than the no toxic effect. Cell culture studies reveal that SeraSeal is not directly toxic for any cells tested. Thus, drug related toxicity is not expected to be seen in this clinical study.

6.6 Research Design and Methods: This clinical trial will be a difference study where SeraSeal will be used as a liquid, administered by a syringe (300 IU/0.1ml), and compared to standard surgical technique as the control. Patients receiving treatment at Edgardo Rebagliati Martins Hospital, the National Guillermo Hospital, Peruvian Air Force Hospital, and the Military Hospital of Peru will serve as study volunteers. Prior to enrollment in the study, an initial screening test and subsequent studies will take place, including: informed consent, collection and recording of subject demographic information, medical history, current medications, assessment of inclusion/exclusion criteria, physical examination, with blood draws for hematological assessment and coagulation studies for bleeding and time to hemostasis. The location of the study wounds will be invasive. The study wound sites will involve bone and soft tissue.

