This is a single-blinded, parallel, randomized clinical trial, where the primary endpoint is hemostasis. Secondary endpoints will include reduction of blood loss, fewer blood transfusions. There are 18 designated surgical faculty members from Head & Neck, Vascular, Thoracic Cardiovascular, Neurosurgery, Orthopedics, and General Surgery participating in this study, with a minimum of 10 surgical procedures being studied. All of the participating surgeons are highly skilled and have extensive expertise in their surgical specialty.

Randomization: The patients will be randomized within each surgical department by drawing a SeraSeal or Cauterization slip. Which ever slip is drawn the next participating patient having the same surgical procedure will

be given the opposite method to control bleeding at same specific bleeding wound sites.

In this trial, the dosage level of SeraSeal is 3,000 IU/ml, with a maximum expected dosage of 10,000 IU, 50 times less than the pre-clinical toxicity studies¹⁴. After hemostasis is achieved the excess SeraSeal will either be removed through irrigation and suction or absorption onto a surgical sponge. Blood loss will be measured and recorded by reading the volume in the suction canister, or by weighing the blood soaked surgical sponges (1 ml whole blood = 1.04 g). A time to hemostasis is measured from the time when the product or the control is first applied to the wound, until no bleeding or oozing is observed for the entire wound. A nurse will use a stopwatch to record the time to hemostasis. SeraSeal is expected to achieve hemostasis 25% faster than the control. Stopping criteria for treatment in the investigational group will be when hemostasis fails to be achieved within 10 minutes for a particular wound, or at the discretion of the surgeon. If this should happen, the patient will be switched over to standard surgical practices. There are no stopping criteria for the control, since the control employ standard surgical procedures.

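### The protocol sets out to determine safety, but for binary adverse events it fixes only tests of difference, in a trial sized on time to hemostasis, so a non-significant result could be read as evidence of safety

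*Protocol*

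**What the plan says.** Protocol 6.1 gives safety equal standing with efficacy: "This study is designed to determine whether it is safe and effective in achieving hemostasis in different types of wounds". Under 6.5, in the part on what the study will determine, the safety outcomes are named: "The safety will be determined by monitoring outcomes from application: recurrence of bleeding, infection, lack of healing, and presence of hypersensitivity reactions". Section 7.2 lists determining the risk of anaphylaxis among the study's purposes.

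Section 8.2 gives the analysis. For binary outcomes, with adverse events expressly included and fever and pruritus as examples, "we will use chi-square methods to compare conventional versus SeraSeal treatment proportions overall". It adds: "Since the total follow up times may differ between groups, we will also compare rates per person-time of binary outcomes". Some related continuous measures are analysed separately: blood loss and log bacterial titer by factorial ANOVA, and the laboratory values by repeated-measures ANOVA.

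On size, 8.2 says: "The sample size is based on the primary outcome, time to hemostasis". Section 6.9 gives the total: "A total of 200 subjects, are to participate in this study". The protocol states no control rate for any safety outcome, no power for safety, and no tolerable excess or interval for these outcomes.

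**The concern.** A test of difference can raise a signal of harm. When it is not significant, it does not show that harm is absent unless the trial was large enough to have found it. Here the aim asks whether the product is safe, the only analyses named for the binary safety outcomes are tests of difference, and the sample size was set for something else. If the report follows 8.2 as written, the safety purpose could be answered by a table of non-significant p-values. A real increase in infection, recurrent bleeding or hypersensitivity could then be described as no difference between groups.

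**Working it through.** **Inputs from the protocol.** Total 200 (6.9). Allocation is by drawing a slip, after which the next patient having the same procedure is to "be given the opposite method to control bleeding at same specific bleeding wound sites" (6.6), so about 1:1. Section 8.2 gives 20 per group × 2 groups × 5 departments = 200, hence 20 × 5 = 100 per arm. The two-sided 5% level is stated in 8.2 for the primary outcome only.

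**Assumptions.** The same two-sided 5% level for safety; no dropout; control rates from 2% to 20%, because the protocol gives none.

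**The plan's own figure.** There is no safety power to reproduce. The total multiplies correctly. The 20 per group cannot be checked because no SD is given. It implies SD = 7.5 / [(1.960 + 0.842) × √(2/20)] ≈ 8.5 minutes, which says nothing about event rates.

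**Power of the chi-square.** For x and y events in two arms of n = 100, the uncorrected Pearson test rejects when |x − y|/n ÷ √[p̄(1 − p̄) × 2/n] > 1.96, with p̄ = (x + y)/(2n). Power is the sum of the two binomial probabilities over all rejecting pairs.

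| Control v SeraSeal | Power | Missed |
|---|---|---|
| 2% v 4% | 0.114 | 89% |
| 5% v 10% | 0.270 | 73% |
| 10% v 20% | 0.518 | 48% |
| 15% v 30% | 0.729 | 27% |
| 20% v 40% | 0.880 | 12% |

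Check by normal approximation for 5% v 10%: standard error under the null √(2 × 0.075 × 0.925/100) = 0.0372; under the alternative √[(0.05 × 0.95 + 0.10 × 0.90)/100] = 0.0371; z = (0.05 − 1.96 × 0.0372)/0.0371 = −0.62; power 0.27. This agrees.

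A tripling is also often missed at the low end: 2% v 6% has power 0.276 (72% missed) and 5% v 15% has 0.683 (32% missed). With a Yates correction or Fisher's test the miss rates for a doubling are higher: 96% at 2% v 4% with either, and 58% (Yates) or 56% (Fisher) at 10% v 20%.

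**Hypersensitivity.** Section 7.2 cites 2.5% anaphylaxis on second exposure to aprotinin, which SeraSeal does not contain. Used purely as an illustration, with an assumed control rate of zero, the uncorrected test needs at least 4 events against 0. At a true rate of 2.5% the chance of that is 0.241, so it is missed about 76% of the time.

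**What an interval would show.** The Newcombe 95% interval combines the Wilson limits (l, u) of each arm. Its upper limit is d + √[(u₁ − p₁)² + (p₂ − l₂)²] and its lower limit is d − √[(p₁ − l₁)² + (u₂ − p₂)²], where d = p₁ − p₂ and arm 1 is SeraSeal.

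- 10 v 5 events: Wilson limits 5.5% to 17.4% and 2.2% to 11.2%. d = 5.0 points, interval −2.6 to +13.0. The chi-square is 0.05²/(0.075 × 0.925 × 0.02) = 1.80, p = 0.18. The result is non-significant, yet an excess of up to 13 points is not excluded.
- 5 v 5 events: ±√[(0.1118 − 0.05)² + (0.05 − 0.0215)²] = ±6.8 points.
- 0 v 0 events: the Wilson upper limit is 3.7%, so ±3.7 points.

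**The case against.** The strongest reply is that the protocol never makes non-significance the criterion for safety. Section 6.5 speaks of monitoring outcomes, 6.6 has each adverse event graded for relatedness over 30 days, and 8.2 says only that proportions will be compared. Comparing adverse events by chi-square in a trial sized for efficacy is ordinary practice. Interval methods are commonly left to a statistical analysis plan, which is not at hand.

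Much of this stands. A reader might infer that a missed harm would be declared safe; no passage says so, and the supportable statement is that it could be read that way. A reader might also take the safety assessment to rest on chi-square alone. It does not: 8.2 adds person-time rates, and infection and bleeding have continuous counterparts in bacterial titer and blood loss. Nor is missing a doubling half to nine times in ten a general property of the trial. It holds for control rates of about 2% to 10% and fails above them, and higher rebleeding rates are possible because 6.7 admits patients on anticoagulants or with coagulation disorders. Finally, the fix adds no power.

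The point is not disposed of. The person-time and ANOVA analyses are also comparisons for a difference, and with 30 days of participation for everyone, person-time should add little. Section 8.2 names no continuous measure of healing or hypersensitivity. The finding also does not rest on an omitted detail: the protocol itself states the aim of determining safety and itself selects a method that cannot meet that aim when the result is non-significant. A later analysis plan could add intervals, but it would not change how the objective is worded.

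**Conclusion.** The point holds in a limited form. The aim in 6.1, 6.5 and 7.2 and the method in 8.2 do not match for binary safety outcomes: the method can signal harm but cannot support a conclusion of safety, and no other criterion is given.

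The size depends on control rates that the protocol does not state. With 100 per arm, a two-sided 5% level and no dropout, a doubling is missed about 89% to 48% of the time for control rates of 2% to 10%, and about 27% to 12% of the time for 15% to 20%. The documents do not show that non-significance will be reported as safety, only that nothing in them prevents it. The primary efficacy analysis is unaffected. This should be changed, but it does not invalidate the trial.

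**What to change.** In 8.2, for recurrence of bleeding, infection, delayed healing and hypersensitivity, make the risk difference (SeraSeal minus control) with its two-sided 95% Newcombe interval the basis of the safety conclusion. Word that conclusion as the largest excess the interval excludes. State that p > 0.05 will not be taken as evidence of safety, and keep the chi-square comparison as a signal of harm.

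In 6.1 and 6.5, word the safety aim as estimating these excess risks, and indicate the precision 100 per arm can give: about 7 points with 5 v 5 events and about 3.7 points with 0 v 0.

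The cost is a few sentences and a few intervals, with no extra patients or procedures. The change does not make a doubling easier to detect; it makes the remaining uncertainty visible. The price is a more modest safety claim.
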